1.0 INTRODUCTION AND STUDY RATIONALE

Glioblastoma multiforme (GBM) is an extremely heterogeneous tumor with a rapidly fatal outcome with a median overall survival of 14.3 months from diagnosis. In spite of intense basic science research and numerous clinical trials, no therapy has emerged in the last decade that has prolonged the overall survival of GBM patients. Newly diagnosed GBM is currently treated with maximally safe resection followed by radiation therapy (RT) with concurrent temozolomide therapy followed by temozolomide maintenance therapy. Standard of care RT is prescribed to the tumor volume determined by magnetic resonance imaging (MRI) obtained before or immediately after tumor resection. No tumor physiologic information or adaptive tumor changes during RT are currently incorporated into the radiation treatment plan. Standard fractionation (46 Gy in 23 fractions) RT is delivered to the peritumoral abnormal FLAIR volume followed by a sequential boost (14 Gy in 7 fractions) to the T1 contrast-enhancing tumor volume. This approach disregards the biological complexity and intratumoral heterogeneity of this neoplasm in terms of angiogenesis, cellularity, and even the methylation status of the promoter of the O6-methylguanine-DNA-methyltransferase (MGMT) gene, which has been shown to be predictive biomarker of response to conventional RT. In addition, the prescribed radiation dose is delivered to the tumor and peritumoral areas over 6 weeks without monitoring response of the tumor during this treatment period. As a consequence, opportunities to readjust radiation dose, for example during the boost phase, to more radio-resistant areas in order to potentially prolong RT response of this extremely heterogeneous tumor are missed. Additionally, if the tumor becomes smaller in volume in response to RT, unnecessarily larger dose is given to potentially normal brain areas.

The study is designed to assess the time course and magnitude of dynamic changes of morphology and distinct physiologic properties of GBM during and after completion of hypo-fractionated RT. MRIs obtained during therapy will be used to quantify during therapy patterns of dynamic changes of distinct physiological properties in response to RT. MRI obtained at completion will be used to quantify total effect of radiation to the tumor. Combined with follow-up evaluations of site of recurrence, progression time and overall survival, this study can establish quantitative imaging based biomarker of favorable treatment response and treatment resistance. These quantitative imaging biomarkers can be utilized to adopt a more scientific, quantitative tumor physiology based dynamic adaptive radiation planning compared to the current practice of pre-treatment anatomy-based fixed dose RT. This approach of adaptive radiation can potentially allow dynamic readjustment of the dose to the relatively less responding tumor areas with simultaneous integrated boost, readjusting the target volumes or opt for an alternative radiation techniques and use of radiosensitizers as 6-week long RT progresses. In addition, our proposed

quantitative techniques can identify tumors poorly responding to RT that can allow institution of early additional or alternative therapy rather than waiting the tumors to recur, the current clinical standard. In addition to significant impact in planning RT, these quantitative imaging biomarkers can be used to predict response to RT, progression time, site of recurrence and overall survival.

As no imaging is performed during the 6 weeks long course of hypo-fractionated RT of GBM, imaging changes of the contrast enhancing tumor volume and peri-enhancing abnormal FLAIR volume related to RT are currently not known. There is no documentation of progressive change in tumor volume as therapy progresses. Neither is it known if there are progressive changes of tumor physiology with continued RT. It is also not known if the entire enhancing tumor volume and the entire non-enhancing tumor volume of this extremely heterogeneous tumor responds similarly to the prescribed radiation dose. We want to evaluate the morphologic as well as physiologic changes in response to radiation therapy in combination with temozolomide as described below:

Morphologic changes: There are progressive changes of the size as RT progresses in cancers of other organ. As for example, in head and neck cancers with hypo-fractionated RT causes reductions of 51% in the clinical target volume and 48% in the planning target volume after a partial course (45-Gy dose) of RT.¹ However, we expect that there may be actual worsening of both the enhancing volume and the peritumoral abnormal FLAIR volume secondary to radiation induced release of cytokines and vasodilation.²

Post contrast 3DT1 weighted sequence and 3d FLAIR sequence is routinely used to calculate different target volumes and can be used to quantify morphologic changes of the enhancing tumor volume and peri-enhancing abnormal FLAIR volume as therapy progresses.

Physiologic changes:

Diffusion-weighted MRI (DWI) is an MRI method that produces *in vivo* images of biologic tissues based on the detection of a change in the random motion of water protons.^{3,4} Free and random diffusion of water is impeded by cell membrane that is an integral part of the cellular architecture.⁵ Apparent diffusion coefficient (ADC) map, one of the many different parameters calculated from diffusion imaging, represents a measure of average water diffusion for each voxel.⁶ As tumor cellularity increases with increasing grade of a tumor, the impeding effect of cell membranes on water diffusion is expected to increase, resulting in lower total diffusion in a given voxel and thus decreasing the ADC value. An inverse correlation exists between tumor cellularity and ADC value.⁷ Lower ADC value has been associated with poor survival independent of the WHO grading status of the astrocytomas.⁵ During routine follow-up of GBM patients after completion of RT, an ADC value of

$\leq 1.09 \text{ } 10^{-3} \text{ mm}^2 \text{ s}^{-1}$ has been shown to differentiate radiation related changes from recurrent tumor.⁸

Perfusion MRI is a technique that can provide physiologic information about vascular endothelial proliferation, vascular density, and angiogenesis.⁹ Vascular proliferation is an important factor in the biology of GBM, and degree of new blood vessel formation increases with higher grades of tumor. Since DSC perfusion MRI can assess new vessel formation, it has been successfully used to assess grading of the astrocytomas¹⁰ and prediction of survival. In fact higher normalized CBV, a parameter generated from DSC perfusion MRI correlates with survival regardless of WHO grading status of the tumor. Tumors with a high initial relative CBV have more rapid progression than those who have gliomas with a low relative CBV.¹¹ Fractional tumor burden can be calculated from the perfusion MRI that can reliably differentiate radiation related changes from residual tumor.¹²

MR spectroscopy is a powerful tool in investigating tumor biology.¹³ Specifically, elevation in choline (Cho) with depression of N-acetylaspartate (NAA) is a reliable indicator of tumor. Metabolite ratios of Cho/creatinine (Cr), NAA/Cr, and Cho/NAA are useful in grading tumors and predicting tumor malignancy.¹⁴ In addition, there is direct correlation between Cho level and cellular proliferative index.^{15,16} MR spectroscopy has also been used to differentiate radiation related changes from recurrent tumor in the post-treatment setting. CNI >1.8 has been shown to reliable differentiate tumor from radiation related changes with sensitivity of 84%, specificity of 75% and diagnostic accuracy of 81%.¹⁷

2.0 OBJECTIVES

Primary:

Determine the time course and magnitude of MRI measures of enhancing volume, (with 3DT1), non-enhancing abnormal FLAIR volume (with 3D FLAIR), tumor cellularity (with ADC), tumor angiogenesis (with nCBV), and chemical environment of enhancing and non-enhancing tumor during the course of hypofractionated RT.

Secondary:

Determine whether multi-parametric imaging assessment during RT and immediately after completion of RT can predict time to recurrence, site of recurrence and overall survival.

Determine whether imaging changes in tumor with methylated MGMT promoter region differs from tumors with unmethylated MGMT promoter region.

3.0 STUDY DESIGN OVERVIEW

3.1 Study Design

Patient source: Once the study is funded, consecutive 20 patients with newly diagnosed GBM patients scheduled to have RT will be included in the study with the following inclusion and exclusion criteria. The patients will be screened from the radiation oncology department schedule.

Patient selection

Inclusion criteria:

- 1) Newly diagnosed primary GBM, based on pathology confirmation;
- 2) At least 8 cm³ of residual enhancing tumor after surgery (As seen on immediate postoperative scan);
- 3) Scheduled to receive standard fractionated RT with concomitant temozolomide therapy;
- 4) Karnofsky Performance Score > 60.

[figure not shown]
Exclusion criteria:

- 1) Scheduled to receive investigational chemotherapy, immunotherapy, or any other investigational agents;
- 2) Placement of GLIADEL® wafer in the resection cavity;
- 3) Significant amount of hemorrhage within the resection cavity (seen on immediate post-operative scan);
- 4) A large peritumoral infarction related to surgery (identified by new confluent diffusion restriction);
- 5) Not suitable to undergo MRI or use the MRI contrast agent (GFR<30 mL/min/1.73 m²); or the patient has known anaphylactic reaction to gadolinium based contrast agents.
- 6) Presence of serious systemic illness, including: uncontrolled infection, uncontrolled malignancy, significant renal disease, or psychiatric/social situations, which might impact the survival endpoint of the study or limit compliance with study requirements.

Patient Accrual Process: Once eligibility criteria have been assessed and the informed consent is obtained, participants will undergo a screening process to further ensure eligibility. Screening prior to registration will comprise a review of pathology reports, postoperative MR images, operative reports, and medical history; general physical and neurologic exams; routine blood work; and urine pregnancy test for women of childbearing age.

Radiation Treatment: RT will be prescribed as per the discretion of the treating radiation oncologist as per the University of Alabama at Birmingham Department of Radiation Oncology treatment protocol in combination with temozolomide. The target volumes will be contoured in the conventional way based on the pre-surgery standard of care MRI in combination with the immediate post surgery MRI obtained within 1-2 days after surgery. Enhancing volume will be treated with 60 gray and non-enhancing tumor volume will be treated with 46 Gy with daily 2 Gy hypo-fractionated regimes. The margin of the abnormal FLAIR volume will be decided at the discretion of the prescribing radiation oncologist. Multiple MRIs obtained, as a part of this research project will not be used in clinical decision-making. **Precisely, there will be no change in the prescribed radiation dose, or the radiation planning based on the MRIs obtained during treatment.** The patient will be taken care of and followed as per the department protocol.

Figure 1 – Study Design

Timing of acquisitions: The following MRI sequences will be obtained at the baseline (scan#1) (the previous day or on the day of starting RT) after completion of 20 Gy (scan#2), after completion of 40 Gy (scan#3) and after completion of 60 Gy (scan#4). All the following imaging sequences will be with a 3T Siemens MRI system (Siemens Prisma, Siemens AG, Erlangen, Germany).

Imaging parameters:

Precontrast 3DT1 sequence: 3D spoiled gradient echo T1 weighted sequence will be performed using the standard parameters.

3D FLAIR sequence: A 3D FLAIR imaging will be obtained in the sagittal plane using the standard parameters.

Diffusion Imaging: Routine diffusion weighted imaging will be obtained with B1000 using three diffusion gradients in the three orthogonal planes using standard parameters.

Echoplanar spectroscopy imaging: We will obtain point resolved echo-planar spectroscopy using a 20 channel head coil with TE/TR 70/1550 ms with acquisition time of 16 minutes as described by Ding et al.¹⁸ After correction for oversampling in the readout spatial and spectral dimensions, the resultant images were equivalent to 50 x 50 voxels in-plane and 18 slices, over a field-of-view of 280 x 280 x 180 mm, with selection of a slab of 140 mm covering the whole brain. Subsequent to spatial smoothing, the effective voxel volume will be approximately 1 ml. The acquisition will also include a second dataset obtained in an interleaved manner without water suppression and using excitation and gradient-echo observation. This data will provide a water reference signal with identical spatial parameters.

Dynamic contrast enhanced susceptibility weighted perfusion imaging: The dynamic contrast enhanced T1 weighted perfusion imaging will be obtained first to use as proposing. The dynamic contrast enhanced susceptibility weighted perfusion imaging will be obtained during the bolus injection of additional 0.05 mmol/kg Prohance at 4ml/s, followed by a 20 ml saline flush with the following parameters: TR/TE in ms: 1900/40; 192 x 128 acquisition matrix, flip angle of 72°, slice thickness 3 mm, total of 20-24 slices. A total of 60 dynamics will be obtained.

Postcontrast 3DT1 sequence: 3D spoiled gradient echo T1 weighted sequence (exactly similar to the precontrast 3DT1 weighted sequence will be obtained after the 2 perfusion sequences will be performed using the standard parameters.

Image archiving:

All the acquired raw images will be permanently saved in the Department of Radiology PACS system. The post-processed images will be saved in the primary investigator's office computer, which has access only the primary investigator, rather than to the PACS because clinical significance of the processed images is not known at the current time. Additionally, post-processing of the raw data takes significant amount of time and the end result may not be available before completion of radiation therapy.

Patient follow-up

All the patients will be followed up and treated as per the standard of care. Patients will return for clinical evaluation and standard of care imaging approximately 4 weeks from

the completion of the radiation therapy. After that, all the patients will be treated with standard of care maintenance temozolomide therapy and will return every 2 months for clinical evaluation and standard of care imaging. The follow up has been detailed below in the section 6.3.

3.2 Endpoints

Primary:

The primary endpoint for this analysis is based on CNI, which is a continuous variable and will be calculated MR spectroscopy from the 4 scans during radiation. We want to demonstrate how change in CNI correlates with time to progression and overall survival. CNI of GBM is typically very high due to high cellularity. As tumor cellularity is expected to decline with continued radiation therapy, we expect that the CNI will decrease over time as radiation therapy progresses. Pattern of change of CNI from baseline to the end of radiation therapy is expected to correlate time progression and overall survival. The patients will be followed up for 24 months from the diagnosis or until death for the progression data and the overall survival data.

Secondary:

Secondary endpoints include change of volume, change of ADC, and change of CBV. These endpoints including the primary endpoints are anticipated to change simultaneously in response to radiation. Change of tumor volume will be measured using 3D T1 sequence, Change of ADC, a continuous variable, is calculated from diffusion imaging, change of CBV, also a continuous variable, is measured from perfusion MRI. We want to demonstrate how changes in these parameters correlate with time to progression and overall survival.

Exploratory:

The exploratory objectives of this study are to examine the time to first recurrence, evaluate the location of the recurrence, as well as the overall survival. Time to first recurrence is defined as the time from diagnosis to the date of the first documented tumor recurrence. The location of the recurrence will be assessed on the follow-up MRI. Overall survival is defined as the time between the date of diagnosis and the date of death due to any cause. Any subjects who have not died will be censored at the last known alive date.

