8.1 Sample size

There were no formal sample size calculations performed for this study, however based on the anticipated number of subjects (n=20), if we assume the largest changes in volume to be between the first and fourth time points, and consider the paired difference in means with correlation ranging from weak to moderate ($\rho=0.1 - 0.6$) we anticipate having 66-88% power to detect statistically significant differences at the 0.05 two sided level of significance.

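### Section 3.2 relates imaging change to progression and survival without conditioning on the scan 1 value, so starting prognosis and treatment response can be mixed

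*Combined protocol and SAP*

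**What the plan says.** Section 3.2 (Endpoints) states the aim for the primary variable: "We want to demonstrate how change in CNI correlates with time to progression and overall survival". It adds an expectation: "Pattern of change of CNI from baseline to the end of radiation therapy is expected to correlate time progression and overall survival". For the other markers it says "Secondary endpoints include change of volume, change of ADC, and change of CBV", and gives them the same aim of correlation with outcome. Whether change means an absolute difference, a percentage or a slope is not defined.

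Section 2.0 has a broader secondary objective: "Determine whether multi-parametric imaging assessment during RT and immediately after completion of RT can predict time to recurrence, site of recurrence and overall survival".

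Section 8.0 gives paired t-tests and possibly repeated-measures ANOVA for change over time, Kaplan-Meier curves without covariates, and possible chi-square tests and logistic regression for site of recurrence. It gives no model linking imaging to time to progression or survival, and nowhere is the scan 1 value named as a covariate.

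On the prognostic meaning of the starting level, section 1.0 says of CBV: "Tumors with a high initial relative CBV have more rapid progression than those who have gliomas with a low relative CBV". Of ADC it says: "Lower ADC value has been associated with poor survival independent of the WHO grading status of the astrocytomas", without naming a time point. CNI appears there as a diagnostic cutoff: "CNI >1.8 has been shown to reliable differentiate tumor from radiation related changes".

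**The concern.** A patient with a high scan 1 value will, on average, show a larger fall by scan 4 whether or not the tumour responded. If a high starting value also carries a worse prognosis, as the protocol says of CBV, large falls will tend to accompany early progression for reasons unrelated to response. That works against the study's hypothesis that a fall is favourable. For ADC the unfavourable value is the low one, so the sign flips but the mixing is the same.

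The consequence would be a useful marker discarded, or one reported with the wrong sign. Choosing a Cox model or a rank correlation would not cure this, because the difficulty lies in the predictor. The results are intended as preliminary data for grant applications and for publication (section 11.2).

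**Working it through.** **1. The plan's own figure.** Section 8.1 gives 66-88% power with n = 20 and correlation ρ from 0.1 to 0.6, but no mean change and no SDs. For a paired t-test with equal SDs, a mean change of 0.75 SD gives 66% at ρ = 0.1 but 94.5% at ρ = 0.6. A mean change of 0.66 SD gives 88% at ρ = 0.6 but 55% at ρ = 0.1. Both ends fit if the two SDs differ by about 2:1 in either direction. The figure is therefore neither confirmed nor shown wrong. It concerns within-patient change in volume, so it does not bear directly on the association with outcome. What is borrowed from it is the range of ρ: "consider the paired difference in means with correlation ranging from weak to moderate".

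**2. The tie between change and baseline.** Let change D = Y4 - Y1 and k = SD at scan 4 / SD at scan 1. Then corr(D, Y1) = (ρk - 1) / √(1 + k² - 2ρk).

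- k = 1: the formula reduces to -√((1 - ρ)/2). At ρ = 0.1 this is -√0.45 = -0.67; at ρ = 0.6 it is -√0.20 = -0.45.
- k = 0.5: -0.89 to -0.87.
- k = 2: -0.37 to +0.12.
- The tie vanishes only at k = 1/ρ.

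A slope over the four scans does not escape it. With equal SDs, equal correlations and weights -3, -1, 1, 3, corr(slope, Y1) = -3√((1 - ρ)/20), which is -0.64 at ρ = 0.1 and -0.42 at ρ = 0.6.

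**3. What this does to the estimate.** Let b_base be the log HR per SD of baseline with change held fixed, and b_change the log HR for change given baseline. At k = 1 the regression slope of Y1 on D is -(1 - ρ)/(2(1 - ρ)) = -0.5. To a linear approximation the change-only log HR is therefore b_change - b_base/2, for any ρ.

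**4. Spurious association.** Inputs from the documents: n = 20, median survival 14.3 months (section 1.0), follow-up 24 months (sections 3.2 and 6.3), two-sided 0.05 (section 8.0). Assumed: exponential survival, k = 1, and the baseline log HR. Expected deaths are 20 × (1 - 2^(-24/14.3)) = 20 × 0.688, or about 13.8; the simulations with a prognostic baseline averaged about 13 to 13.7. Share of simulated trials (1,000 to 2,000 per setting) with a significant Cox test for change when b_change = 0:

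| Assumed b_base | Change alone, ρ = 0.1 | Change alone, ρ = 0.6 |
|---|---|---|
| 0 | 5% | 4-5% |
| 0.2 | 8% | 5% |
| 0.4 | 13-15% | 8-10% |
| 0.7 | 27-30% | 14-15% |
| 1.1 | 47% | 22% |

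With baseline in the model the rate is about 5-7%. At b_base = 0.7, changing the SD ratio gives 49% at k = 0.5, 33-40% at k = 0.7, and about 6-12% at k = 2.

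**5. Masking.** With b_base = 1.39 and b_change = 0.69, step 3 gives 0.69 - 0.695, or about 0. Change alone is significant in 5% of trials, against 56% (ρ = 0.1) and 39% (ρ = 0.6) after adjustment.

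**6. Reversal.** With b_base = 1.10 and b_change = 0.26, step 3 gives -0.29. The simulated median is -0.23 (ρ = 0.1) and -0.21 (ρ = 0.6), significant in the wrong direction in 17% and 9% of trials. The adjusted medians are +0.30 and +0.28.

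**7. Sample size is not the cause.** At n = 500 with b_base = 0.69 and b_change = 0, the change-only median log HR is still about -0.31.

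**The case against.** A reader might infer that the protocol itself calls baseline CNI prognostic. It does not. Section 1.0 cites CNI to tell tumour from radiation change, and metabolite ratios for grading and malignancy. Nothing is said about prognosis from starting volume either. Only CBV and ADC are supported. Both are secondary endpoints, and both statements concern gliomas or astrocytomas in general, whereas this cohort is glioblastoma with at least 8 cm³ of residual enhancement. This objection stands: for CNI and volume, a prognostic baseline is plausible but assumed.

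A reader might also infer that the plan prescribes an unadjusted analysis. It prescribes no association model at all, and the objective in section 2.0 is wider than change. This stands too. Still, change is the only predictor section 3.2 names, and a literal reading leads to the change-only analysis.

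The rates depend on inputs the documents do not supply. The range of ρ is given for volume only, and no SDs or baseline hazard ratios are given. The masking example sits on a cancellation point. In a different setting, let the part of scan 4 not explained by scan 1 carry a log HR of 0.7 per SD. Change alone is then significant in 4% / 14% of trials (ρ = 0.1 / 0.6) when baseline also carries 0.7, but in 19% / 36% at 0.2 and 35% / 48% at 0. So it cannot be said that a true benefit will be cancelled, only that it can be.

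Finally, a marginal correlation of change with outcome is a legitimate quantity. It is spurious only as a statement about response given the starting level. That is a fair reason to allow the unadjusted result to be shown, but not to make it the main one, since the stated purpose is a biomarker of response.

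**Conclusion.** The point holds in conditional form. Section 3.2 relates change to outcome, no section conditions on scan 1, and change is negatively tied to baseline unless the spread rises strongly by scan 4. Where the starting level is prognostic, a change-only result mixes that prognosis with response.

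For n = 20 and equal SDs, the change-alone false-positive rate is about 28% (ρ = 0.1) or 14% (ρ = 0.6) at an assumed baseline log HR of 0.7 per SD. It is about 13% or 9% at 0.4, and nominal if baseline is not prognostic. It grows if the SD falls by scan 4 and shrinks if it doubles. The true size for this trial cannot be determined from the documents.

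A reader might take this as a flaw that invalidates the study. That is too strong: section 8.0 describes the analysis of 20 patients as mainly descriptive, and section 3.4 keeps the scans out of clinical decisions. It is a correction that should be made before analysis because it costs almost nothing.

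**What to change.** In sections 3.2 and 8.0, state that every analysis relating an imaging change to time to progression or overall survival includes that marker's scan 1 value as a covariate; entering scan 1 and the later scan together is equivalent when change is an absolute difference. Define the form of change. Report the change effect given baseline, with its 95% CI, as the main result, labelled exploratory. The unadjusted association may be shown beside it, but not as the main result.

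The cost is a sentence in each section and one model term per marker. No new data are needed, since scan 1 is already scheduled for every patient. The downside is precision: two covariates on about 13-14 deaths is roughly 7 deaths per covariate (13.8 / 2 = 6.9), so intervals will be wide and should be presented as such.

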3.3 Study Duration and Dates

Study Inclusion: 9 months

Study duration: 3 years

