4.0 SELECTION OF PATIENTS

4.1 Number of Patients

Approximately 20 patients should be enrolled and treated in this study. It is planned to recruit this sample in 9 months.

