6.3 Follow-up

The final intervention as a part of this research study is to acquire the 4th MRI, which we plan to obtain at the completion of the current clinical standard of care radiation therapy. No therapy is part of this study. However, all included subjects will be followed-up for 24 months from the time of diagnosis. During the follow-up period each patient will be imaged and evaluated according to clinical standard of care. We will document the followings:

Progression: We will assess time to progression as well as site progression.

Progression will be determined by the RANO¹⁹ criteria as described in the Table 1:

Criteria for Determining First Progression Depending on Time From Initial Chemoradiotherapy

First Progression	Definition
Progressive disease < 12 weeks after completion of chemoradiotherapy	Progression can only be defined using diagnostic imaging if there is new enhancement outside of the radiation field (beyond the high-dose region or 80% isodose line) or if there is unequivocal evidence of viable tumor on histopathologic sampling (eg, solid tumor areas [ie, > 70% tumor cell nuclei in areas], high or progressive increase in MIB-1 proliferation index compared with prior biopsy, or evidence for histologic progression or increased anaplasia in tumor). Note: Given the difficulty of differentiating true progression from pseudoprogression, clinical decline alone, in the absence of radiographic or histologic confirmation of progression, will not be sufficient for definition of progressive disease in the first 12 weeks after completion of concurrent chemoradiotherapy.
Progressive disease ≥ 12 weeks after chemoradiotherapy completion	
 • New contrast-enhancing lesion outside of radiation field on decreasing, stable, or increasing doses of corticosteroids. • Increase by ≥ 25% in the sum of the products of perpendicular diameters between the first postradiotherapy scan, or a subsequent scan with smaller tumor size, and the scan at 12 weeks or later on stable or increasing doses of corticosteroids. • Clinical deterioration not attributable to concurrent medication

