8.0 STATISTICAL METHODS

Version 1.3; Date: 3/14/2016

Based on the number of subjects (n=20), our statistical analysis will be largely descriptive and explanatory. Descriptive summary statistics tabulations will be generated for each time point. Means, standard deviations, median, and interquartile ranges will be generated for continuous variables, and frequency and percentages will be generated for categorical variables. For the primary outcome variable, in order to evaluate the within-subjects changes over time we will assess the pair-wise differences between time points using paired t-test, and may also perform repeated measures analysis of variance (ANOVA) on the continuous outcomes and account for the correlative nature of the repeated measurements with the caution and understanding of the limited sample size.

The Kaplan-Meier approach will be used to produce survival curves as well as the median and corresponding 95% confidence limits for time to first recurrence as well as overall survival. Subjects who have not had an event will be censored at the last known date available.

The location of recurrence will be reviewed and classified to then be presented in terms of frequencies and percentages to determine if there can be any dichotomization scheme created. Based on the potential dichotomization, we may use chi-square tests and logistic regression to examine how other factors may be potentially associated with the site of recurrence.

Distributional assumptions of the statistical analysis will be verified, and if the assumptions are not met, then non-parametric analogs will be considered. Statistical significance will be determined based on the two-sided level of significance at the 0.05 level. All analyses will be performed using statistical analysis software SAS version 9.4.

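### Overall survival follow-up ends at each patient's own 24 months with no common cut-off date; one calendar cut-off would cheaply make the planned upper 95% limit for the median more often estimable

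*Combined protocol and SAP*

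**What the plan says.** Section 3.2 sets the follow-up: "The patients will be followed up for 24 months from the diagnosis or until death for the progression data and the overall survival data". Section 6.3 agrees: "all included subjects will be followed-up for 24 months from the time of diagnosis".

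Section 8.0 promises Kaplan-Meier curves "as well as the median and corresponding 95% confidence limits for time to first recurrence as well as overall survival".

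The censoring text is looser than the follow-up text. Section 3.2 censors patients who have not died at the date they were last known to be alive. Section 8.0 censors patients without an event at the last date available. Neither gives a calendar cut-off, and neither orders censoring at month 24.

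On size and timing, section 4.1 says "Approximately 20 patients should be enrolled and treated in this study" and "It is planned to recruit this sample in 9 months", and section 3.3 says "Study duration: 3 years". The only survival figure in the document is in section 1.0: "median overall survival of 14.3 months from diagnosis".

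Section 3.1 describes standard-of-care visits every 2 months during maintenance therapy, with no stated end. Section 6.3 records only survival time after first recurrence.

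**The concern.** Patients enter over 9 months, so when the last one reaches 24 months from diagnosis, the first could have been observed for up to about 33 months. The plan has no procedure for collecting that extra time. Two readings are possible. Either everyone stops at 24 months, or later dates are used where they happen to be on file. The second is not harmless: deaths are noticed more readily than continued survival, and uneven late ascertainment can bias the curve.

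What is at stake is the upper confidence limit for median overall survival. With 20 patients and about 14 expected deaths, it sits at the edge of being estimable. Overall survival is listed as exploratory in section 3.2, but section 2.0 makes predicting it a secondary objective, and section 3.2 wants the change in CNI, the primary endpoint, correlated with it. Deaths are therefore worth having, although the number gained is small.

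**Working it through.** The plan states no expected number of deaths and no survival precision, so there is no figure of its own to reproduce. The power range in section 8.1 concerns volume change and does not bear on this point.

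**Inputs.** From the document: n = 20 (4.1), median 14.3 months (1.0), stop at 24 months from diagnosis (3.2, 6.3), accrual 9 months (3.3, 4.1), two-sided 95% limits (8.0). Assumed: Weibull survival with shape 1.0 (exponential), 1.3 or 1.5; alternative medians of 10, 12 and 16 months; entry uniform over 9 months, close to diagnosis; no loss to follow-up. The document gives no hazard shape and no dropout rate.

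**Step 1: deaths needed.** If all 20 are followed to 24 months and k have died, S = 1 − k/20. The Greenwood sum is k/[20(20 − k)], and the log-log upper limit is S^exp(−1.96·se), where se = √(Greenwood sum)/|ln S|.

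- k = 14: S = 0.30, sum = 14/120 = 0.1167, se = 0.3416/1.2040 = 0.2837, upper limit 0.501.
- k = 15: S = 0.25, sum = 15/100 = 0.15, se = 0.3873/1.3863 = 0.2794, upper limit 0.449.

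The upper limit for the median exists only once the upper limit for S falls to 0.5, so 15 deaths are needed. The linear interval also gives 0.501 at 14 deaths.

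**Step 2: chance of falling short at 24 months.** S(24) = exp[−ln 2·(24/m)^shape] for median m. For m = 14.3 and shape 1, S(24) = 0.312. Expected deaths are 20 × 0.688 = 13.75, and the binomial P(14 or fewer deaths) = 0.63. For shape 1.5, S(24) = 0.222, expected deaths are 15.6 and the probability is 0.27.

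**Step 3: common calendar cut-off.** Stopping when the last patient reaches 24 months gives individual follow-up spread over 24 to 33 months. I simulated 40,000 trials per cell with log-log limits. The cells below show the share of trials with no estimable upper limit.

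| Median | Shape | Stop at 24 months | Common cut-off | Expected deaths |
|---|---|---|---|---|
| 14.3 | 1.0 | 63% | 29% | 13.8 → 14.9 |
| 14.3 | 1.3 | 41% | 9% | 14.9 → 16.3 |
| 14.3 | 1.5 | 27% | 3% | 15.6 → 17.1 |
| 12 | 1.0 to 1.5 | 38% to 5% | 13% to under 1% | 15.0 → 16.1 (shape 1.0) |
| 10 | 1.0 to 1.5 | 16% to under 1% | 4% to 0% | 16.2 → 17.2 (shape 1.0) |
| 16 | 1.0 to 1.5 | 77% to 50% | 43% to 11% | 12.9 → 14.1 (shape 1.0) |

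**Step 4: sensitivity to n.** Section 4.1 says approximately 20. At a 14.3-month median with shapes 1.0/1.3/1.5 and a 24-month stop:

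- n = 18 (13 deaths suffice): 51/31/19%.
- n = 20 (15 deaths needed): 63/41/27%.
- n = 21 (15 deaths suffice): 50/28/16%.

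**Step 5: the median itself.** It is missing only if fewer than 10 of 20 die. At 14.3 months, exponential, that is about 2%.

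**Step 6: timeline.** 9 + 24 = 33 months, which leaves 36 − 33 = 3 months for analysis.

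**The case against.** A uniform 24-month window is a legitimate design. Every patient has the same observation time, and the 24-month survival estimate is clean. An upper limit reported as not reached is a valid Kaplan-Meier result, the analysis is described as largely descriptive, and the median is almost always available. All of this stands, and it is why the point is an improvement and not a fault.

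The percentages are also fragile. At n = 20, 14 deaths miss the criterion by 0.001, and one patient more would remove that. Eligibility requires at least 8 cm³ of residual enhancing tumor, so survival may be shorter than 14.3 months, which shrinks the problem. This stands too, and only the ranges should be quoted.

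The common cut-off adds little more than one death, so it does not guarantee the limit and helps the imaging-survival association only modestly. This also stands.

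Three stronger readings are tempting but unsupported:

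- **An idle third year.** A reader might set 24 months against a 3-year study. Accrual and follow-up already take 33 of the 36 months, and the rest is needed for analysis.
- **The plan throws data away.** The censoring wording in 3.2 and 8.0 does not require truncation at month 24. What is missing is systematic collection to a stated date.
- **The later data are already held and cost nothing.** The document prices nothing and does not show that vital status is known after month 24. That the cost is low is an inference from standard-of-care visits and survival-only recording after recurrence.

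**Conclusion.** The point holds as a low-cost gain in precision. Under the stated 24-month follow-up, and at the protocol's own median with exactly 20 patients, the planned upper limit would be inestimable in about 27-63% of trials. A common calendar cut-off brings this to about 3-29% and adds about 1.2-1.5 deaths. It helps in every scenario where the limit is appreciably at risk. At a 10-month median with a rising hazard there is almost nothing to gain.

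The result rests on the 14.3-month median applying to this cohort, Weibull shapes between 1.0 and 1.5, even accrual and complete follow-up. The document supports only the first of these, and only as a general figure for the disease. It would go too far to say that the survival analysis fails or that the plan contradicts itself.

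**What to change.** - **Sections 3.2 and 6.3:** for overall survival, replace the individual 24-month stop with vital status collected for all patients up to one calendar date, namely when the last enrolled patient reaches 24 months from diagnosis (about study month 33). Censor survivors at the last date known alive, no later than that date. Progression follow-up may stay at 24 months.
- **Section 8.0:** align the censoring sentence with this, stating the cut-off for survival and the one for recurrence separately.

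**Cost:** a small amendment and a vital-status check on the patients alive at 24 months, about 20 × 0.222 = 4 to 20 × 0.312 = 6 of them. No study scan or visit is added. Follow-up times become unequal, which Kaplan-Meier handles, and survival at 24 months can still be reported. The investigator should confirm that the consent covers vital-status checks after month 24; the consent pages were not available for this review.
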